3.5.7 Subgroup Analyses

Safety summary tables and summary of AE by SOC/PT will be repeated for the following subgroups:

- OAK-LIKE Population
- Demographics:
 - Age (<, ≥ 65 years),
 - Age (<, ≥ 80 years),
 - Region (Europe, Asia, LATAM)
- Baseline disease characteristics:
 - Histologic subtype (squamous, non-squamous),
 - ECOG performance status at baseline (0/1, 2),
 - Brain metastases at baseline (yes, no)
 - Liver metastases at baseline (yes, no),
 - History of autoimmune disease (yes, no),
 - Prior anti-PD-1 therapy (yes, no),
 - Renal impairment (eGFR $<$, ≥ 60 mL/min/m²),
 - EGFR positive at baseline (yes, no),
 - ALK positive at baseline (yes, no),
 - Active hepatitis B or C at baseline (positive, negative),

3.5.8 Laboratory Data

Laboratory parameters will be summarized by using shift table of baseline versus worst post-baseline category (grade for gradable parameters as per NCI CTCAE version 4.0 and low/normal/high for non-gradable parameters). The first abnormal category for patients with High and Low for the same laboratory test (at different visits) will be considered. A “Missing” category will be reported for subjects with missing grades or missing reference range indicators at baseline and/or post-baseline and subjects with no laboratory assessments.

In addition, a summary table will be provided for clinically relevant laboratory shifts from baseline defined as shifts from Grade 0, 1, or 2 at baseline to Grade 3 or 4 post-baseline.

All laboratory values will be listed. Separate listings will be generated to include all abnormal laboratory values for hematology, biochemistry, coagulation and thyroid function.

3.5.9 **Vital Signs and ECOG Performance Status**

Vital Signs of each patient, actual value and change from baseline for vital signs parameters will be summarized using descriptive statistics. ECOG PS will be summarized in a shift table of baseline versus worst post-baseline value.

3.6 **MISSING DATA**

For the flagging of a treatment emergent adverse event or concomitant medication with partial start and/or end date: the AE/medication will be assumed to be treatment-emergent/concomitant if it could possibly have started or been taken after the first dose of study drug.

Imputation of partial/missing death date will be done as follows:

- If the date is completely missing, then the day of “Last known to be alive” +1 will be used
- If only day is missing and year and month are same as “Last known to be alive”, then the day of “Last known to be alive”+1 will be used otherwise the 1st day of the month will be used
- If day and month are missing and year is same as “Last known to be alive”, then the “Last known to be alive”+1 will be used, otherwise 1st of January will be used

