5.2.3 Adverse Events of Special Interest (Immediately Reportable to the Sponsor)

Adverse events of special interest are required to be reported by the investigator to the Sponsor immediately (i.e., no more than 24 hours after learning of the event; see Section [5.4.2](#) for reporting instructions). Adverse events of special interest for this study include:

- Pneumonitis
- Colitis
- Endocrinopathies: diabetes mellitus, pancreatitis, adrenal insufficiency, hypothyroidism, hypophysitis or hyperthyroidism
- Hepatitis, including AST or ALT > 10 x ULN
- Systemic lupus erythematosus
- Neurologic disorders: Guillain-Barré syndrome, myasthenia gravis, meningoencephalitis
- Nephritis
- Events suggestive of hypersensitivity, infusion-related reactions, cytokine-release syndrome, HLH, and MAS
- Cardiac disorders – Grade ≥ 2 in severity (e.g., atrial fibrillation, myocarditis, pericarditis)
- Vasculitis
- Myositis
- Myopathies, including rhabdomyolysis
- Ocular toxicities (e.g., uveitis, retinitis, optic neuritis)
- Autoimmune hemolytic anemia
- Severe cutaneous reactions (e.g., Stevens-Johnson syndrome, dermatitis bullous, toxic epidermal necrolysis)
- Cases of potential drug-induced liver injury that include an elevated ALT or AST in combination with either an elevated bilirubin or clinical jaundice, as defined by Hy's law (see Section [5.3.5.7](#))
- Suspected transmission of an infectious agent by the study drug, as defined below:
Any organism, virus, or infectious particle (e.g., prion protein transmitting transmissible spongiform encephalopathy), pathogenic or non-pathogenic, is

considered an infectious agent. A transmission of an infectious agent may be suspected from clinical symptoms or laboratory findings that indicate an infection in a patient exposed to a medicinal product. This term applies only when a contamination of the study drug is suspected

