In addition, to adapt to information that may emerge during the course of this study, the Sponsor may choose to conduct one interim analysis for reporting and publication of safety and efficacy results.

Appendix 2

Schedule of Assessments

	Screening Period		Treatment Period Day 1 (\pm 5 days) of each 3-week treatment cycle	Treatment Discontinuation \leq 30 days from last dose or at initiation of new anti-cancer therapy (whichever occurs first)	Follow-Up Period
	Day -28 to Day -1	Day -14 to -1			
Informed consent ^a	x				
Review of eligibility criteria	x				
Medical history and demographics ^b	x				
Weight	x		x	x	
Height	x				
Complete physical examination ^c	x			x	
Limited physical examination ^{c, d}			x ^d		
ECOG Performance Status ^e	x		x ^d	x	
Vital signs ^f	x		x	x	
12-lead ECG ^g	x		as clinically indicated		
HIV, HBV, HCV serology ^h	x		as clinically indicated		
Hematology ⁱ		x	x ^d	x	
Coagulation (aPTT, INR)		x		x	
Thyroid function testing ^j		x	Cycle 2, Day 1, then every other cycle		
Serum chemistry ^k		x	x ^d	x	
Urinalysis ^l		x	x ^d	x	
Pregnancy test ^m		x	Every 3 cycles		

	Screening Period		Treatment Period	Treatment Discontinuation	Follow-Up Period
	Day -28 to Day -1	Day -14 to -1	Day 1 (\pm 5 days) of each 3-week treatment cycle	\leq 30 days from last dose or at initiation of new anti-cancer therapy (whichever occurs first)	
Tumor assessment ⁿ	x ^o		Every 6 weeks for 48 weeks, thereafter every 9 weeks until PD (regardless of atezolizumab discontinuation) or until loss of clinical benefit for patients treated beyond progression ^p		
EGFR/ALK testing ^q	x				
Submission of pre-treatment tumor tissue (biomarker) ^{r,s}		x ^u			
Plasma for RBR (optional) ^t		x ^u		PD	
EORTC QLQ-LC13 & EQ-5D-5L ^v			Day 1 of first 3 cycles, then with tumor assessments		
Concomitant medications ^w	x		x	x	
Adverse events ^x	x		x	x	x
Study drug infusion			x		
Survival and new anti-cancer therapy ^y				x	x

Abbreviations: aPTT: activated partial thromboplastin time; ECG: electrocardiogram; ECOG: Eastern Cooperative Oncology Group; EORTC: European Organisation for Research and Treatment of Cancer; INR: international normalized ratio; PD: progressive disease; PRO-CTCAE: Patient-Reported Outcomes Version of the Common Terminology Criteria for Adverse Events

Note: Unless otherwise indicated, assessments scheduled on the study treatment days should be performed prior to initiation of study treatment infusion.

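### The laboratory shift table keeps only the first abnormal direction when a test goes both low and high, so later opposite shifts are undercounted

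*SAP*

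**What the plan says.** SAP section 3.5.8 sets the main laboratory summary: "Laboratory parameters will be summarized by using shift table of baseline versus worst post-baseline category". The categories come from two scales: "grade for gradable parameters as per NCI CTCAE version 4.0 and low/normal/high for non-gradable parameters". A further sentence deals with patients who are abnormal in both directions: "The first abnormal category for patients with High and Low for the same laboratory test (at different visits) will be considered". The section plans no shift table by direction and no category for patients who were both low and high.

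One other laboratory summary is planned, restricted to "shifts from Grade 0, 1, or 2 at baseline to Grade 3 or 4 post-baseline". All laboratory values are to be listed by patient, and the section adds: "Separate listings will be generated to include all abnormal laboratory values for hematology, biochemistry, coagulation and thyroid function".

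Two other places give context. After screening, thyroid function is tested at "Cycle 2, Day 1, then every other cycle" (schedule of assessments, SAP Appendix 2 and Protocol Appendix 1). Protocol section 5.2.3 includes among the adverse events of special interest (AESIs) "Endocrinopathies: diabetes mellitus, pancreatitis, adrenal insufficiency, hypothyroidism, hypophysitis or hyperthyroidism".

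**The concern.** The table is labelled by severity, but for a patient with both a low and a high value the entry is decided by time order. Each such patient contributes one direction only, and the direction dropped is always the later one. The stated aim of the study is long-term safety, so a rule that systematically discards later findings works against the purpose of the table.

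Thyroid function is a natural illustration. It is measured repeatedly, so both directions can be seen in one patient, and hypothyroidism and hyperthyroidism are both AESIs. What is at stake is the count of patients ever low, or ever high, on a given test. A reader will usually take that count straight from the shift table.

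**Working it through.** The documents give no figure on this point, so there is nothing to reproduce. The check applies the rule to simple patient sequences, asks whether another summary restores what is lost, and then sizes the loss under a stated assumption.

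**Step 1. Apply the rule.** Inputs: the category scale and the first-abnormal rule in SAP section 3.5.8. The last two columns show what summaries by direction would record.

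| Baseline | Post-baseline order | SAP rule | Low summary | High summary |
|---|---|---|---|---|
| Normal | Low, then High | Normal to Low | Normal to Low | Normal to High |
| Low | Low, then High | Low to Low | Low to Low | Low to High |
| Normal | High, then Low | Normal to High | Normal to Low | Normal to High |

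In the first and third rows one of two real shifts disappears. In the second row a real shift from low to high is shown as no change.

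**Step 2. Look for recovery in another summary.** The second laboratory table needs CTCAE grades, so it cannot restore a low or high shift for a parameter that has no grades. The listings keep every value but give no count.

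**Step 3. Size the loss for one test.** Inputs: N = 600 planned patients (Protocol section 3.1); f = share of patients who go low and later high; g = share who are high without an earlier low. Neither f nor g is in the documents. I assume f from 1% to 10%, and g of 5% or 10% for illustration.

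- High shifts lost = N × f
- Patients ever high = N × (f + g)
- Patients shown as high = N × g
- Fraction of ever-high patients lost = f / (f + g)

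| f | Lost (600 × f) | Ever high / shown, g = 5% | Fraction lost | Ever high / shown, g = 10% | Fraction lost |
|---|---|---|---|---|---|
| 1% | 6 | 36 / 30 | 16.7% | 66 / 60 | 9.1% |
| 2% | 12 | 42 / 30 | 28.6% | 72 / 60 | 16.7% |
| 5% | 30 | 60 / 30 | 50.0% | 90 / 60 | 33.3% |
| 10% | 60 | 90 / 30 | 66.7% | 120 / 60 | 50.0% |

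The same arithmetic applies to low shifts lost in patients who go high and later low. The direction of the error does not depend on f: the rule can only lower the count in the second direction.

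**Step 4. Graded tests.** The sentence is not limited to ungraded parameters. Suppose a test is graded in both directions and a patient has Grade 1 low early and Grade 3 high later. The worst grade is 3, on the high side; the first abnormal category is Grade 1, on the low side. If the sentence governs such a test, the two instructions give different entries for the same patient.

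**The case against.** The strongest reply is that there is no inconsistency at all. High and Low are the labels of the ungraded scale, and on that scale the SAP gives no order between them. Worst is then undefined for a patient with both, and the sentence supplies a needed tie-break. This largely stands. A reader might infer that the section flatly contradicts itself, but the text supports that only if the rule also governs graded two-directional tests, which it neither states nor excludes. What survives is that the tie-break discards one of two real shifts, which summaries by direction would not need to do.

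The second reply is that thyroid toxicity is counted elsewhere. Protocol section 5.3.5.5 makes a laboratory result reportable as an adverse event if it comes with symptoms, changes study treatment, leads to an intervention or is judged clinically significant. Appendix 9 (Table 4) attaches treatment to asymptomatic hypothyroidism, and sends asymptomatic TSH below 0.1 mU/L to guidance that includes withholding atezolizumab. Events managed that way meet the reporting rule. SAP section 3.5.3 tabulates AESIs by preferred term, so a patient with both thyroid events counts under both terms. This also stands. A reader might infer that the rule hides immune-related thyroid toxicity from the trial's results; the documents do not support that. What may stay outside every count is mainly the mild, unmanaged excursion, such as asymptomatic TSH from 0.1 to below 0.5 mU/L, for which Table 4 asks only for monitoring.

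Third, the SAP does not say which tests it treats as ungraded. Thyroid function is therefore an illustration, not an established case.

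**Conclusion.** The concern holds in a limited form and is minor. For low/normal/high parameters, the first-abnormal rule makes the shift table undercount patients ever abnormal in the second direction, and it can present a low-to-high change as no change. For graded two-directional tests the scope is unstated; if the rule applies there, it conflicts with a summary based on the "shift table of baseline versus worst post-baseline category".

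The size cannot be fixed from the documents. The 6 to 60 patients out of 600 per test rest entirely on the assumed 1% to 10% who go low then high, and should not be read as an estimate for any named test.

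A reader might also infer that the main safety result is affected. It is not: the primary endpoints are treatment-related serious adverse events and treatment-related immune-related adverse events (SAP section 3.5.2), and neither uses the shift table. The point concerns one descriptive laboratory summary.

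**What to change.** In SAP section 3.5.8, replace the first-abnormal sentence for two-directional tests. Plan two shift summaries for each: baseline against the lowest post-baseline category, and baseline against the highest. State that a patient may count in both. Apply the same split to tests graded in both directions, with the worst grade taken separately on the low and high sides, and name the parameters treated as two-directional so that the scope is no longer open.

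The change belongs in the SAP, since SAP section 3 says its analyses replace those in the protocol. It uses data already collected. The cost is a short text edit and one extra column set per two-sided test, which makes the laboratory output somewhat longer.

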4. REFERENCES

Kaplan, E. L.; Meier, P. (1958): Nonparametric estimation from incomplete observations. *J. Amer. Statist. Assn.* 53:457–481.

Appendix 1

Protocol Synopsis Version 3

TITLE:	A PHASE III/IV, SINGLE ARM, MULTICENTER STUDY OF ATEZOLIZUMAB (TECENTRIQ) TO INVESTIGATE LONG-TERM SAFETY AND EFFICACY IN PREVIOUSLY-TREATED PATIENTS WITH LOCALLY ADVANCED OR METASTATIC NON-SMALL CELL LUNG CANCER (TAIL)
PROTOCOL NUMBER:	MO39171
VERSION NUMBER:	3
EUDRACT NUMBER:	2017-001409-34
IND NUMBER:	Not applicable
TEST PRODUCT:	Atezolizumab (RO5541267)
PHASE:	Phase III/IV
INDICATION:	Non-small cell lung cancer (NSCLC)
SPONSOR:	F. Hoffmann-La Roche Ltd

Objectives and Endpoints

This study will evaluate the long-term safety and efficacy of atezolizumab in patients with locally advanced or metastatic NSCLC who have progressed following standard systemic chemotherapy (including if given in combination with anti-PD-1 therapy, after anti-PD-1 as monotherapy, or after tyrosine kinase inhibitor [TKI] therapy). Patients with a previously detected sensitizing EGFR mutation or ALK fusion oncogene must have received targeted therapy (TKI) followed by at least one line of standard systemic chemotherapy prior to receiving atezolizumab. Overall, patients should not have received more than two lines of standard systemic chemotherapy. Patients will also be eligible if they discontinued first-line or second-line therapy due to intolerance.

Table 1 Objectives and Corresponding Endpoints

Primary Objective	Corresponding Endpoints
• To evaluate the long-term safety of atezolizumab in previously treated patients with advanced NSCLC	
 • Incidence of serious adverse events (SAEs) related to atezolizumab treatment • Incidence of immune-related adverse events (irAEs) related to atezolizumab treatment
Main Secondary Objective	Corresponding Endpoint
• To evaluate the efficacy of atezolizumab in previously treated patients with advanced NSCLC	
 • Overall survival (OS) rate at 2 years, defined as the proportion of patients remaining alive 2 years after initiation of study treatment

Other Secondary Objectives	Corresponding Endpoints

 • To further evaluate the efficacy of atezolizumab in previously treated patients with advanced NSCLC 	
 • OS, defined as the time from initiation of study treatment to death from any cause • Progression-free survival (PFS), defined as the time from initiation of study treatment to the first occurrence of disease progression or death from any cause, whichever occurs first. PFS will be calculated based on disease status evaluated by the investigator according to Response Evaluation Criteria in Solid Tumors, Version 1.1 (RECIST v1.1) and also by disease status evaluated by the investigator according to modified RECIST • OS rate at 3 years, defined as the proportion of patients remaining alive 3 years after initiation of study treatment • Objective response rate (ORR), defined as the percentage of patients who attain complete response (CR) or partial response (PR) according to RECIST v1.1 and also by disease status evaluated by the investigator according to modified RECIST • Duration of response (DOR), defined as the time from initial response to disease progression or death among patients who have experienced a CR or PR (unconfirmed) during the study. Duration of response will be calculated based on disease status evaluated by the investigator according to RECIST v1.1 and also by disease status evaluated by the investigator according to modified RECIST
Exploratory Objectives	Corresponding Endpoints

 • To further evaluate the long-term safety and efficacy of atezolizumab in previously treated patients with advanced NSCLC 	
 • Safety and efficacy of atezolizumab in subgroups of the study population differentiated according to: 
 Presence of CNS metastases at baseline (yes vs. no) ECOG performance status (0 or 1 vs. 2) Histologic subtype (squamous vs. non-squamous) History of or current autoimmune disease (yes vs. no) Prior anticancer treatment • Progression-free survival from start of new anti-cancer therapy, defined as the time from initiation of new anti-cancer therapy to objective tumor progression on next-line treatment or death from any cause • Objective response rate from start of new anti-cancer therapy, defined as the percentage of patients who attain complete response (CR) or partial response (PR) • Progression-free survival 2 (PFS2), defined as the time from initiation of study treatment to objective tumor progression on next-line treatment or death from any cause

Exploratory Biomarker Objectives	Corresponding Endpoints

 • To assess the role of PD-L1 and other biomarkers in the progression and fundamental biology of advanced NSCLC • To evaluate PD-L1 and other biomarkers (e.g., cancer-related genes) as prognostic biomarkers 	
 • Safety and efficacy of atezolizumab in subgroups of the study population differentiated according to: 
 Expression of PD-L1 protein in tumor tissue Presence/absence of other biomarkers in tumor tissue • Correlations between PD-L1 expression and other biomarkers
Patient-Reported Outcome Objectives	Corresponding Endpoint

 • To evaluate health status utility and HR QoL of atezolizumab in previously treated patients with advanced NSCLC 	
 • EQ-5D-5L index-based and VAS scores • EORTC QLQ-LC13 score

EORTC QLQ-LC13, European Organisation for Research and Treatment of Cancer Quality-of-Life Questionnaire—Supplemental Lung Cancer Module; EQ-5D, EuroQol 5-Dimension Questionnaire; HR QoL, health-related quality of life; VAS, visual analog scale.

Study Design

[figure not shown]
Description of Study

Study MO39171 is a phase III/IV, single-arm, multicenter study of the long-term safety and efficacy of atezolizumab treatment in patients with Stage IIIb or Stage IV NSCLC who have progressed following standard systemic chemotherapy (including if given in combination with anti-PD-1 therapy, after anti-PD-1 as monotherapy, or after TKI therapy). Patients with a previously detected sensitizing EGFR mutation or ALK fusion oncogene must have received targeted therapy (TKI) followed by at least one line of standard systemic chemotherapy prior to receiving atezolizumab. Overall, patients should not have received more than two lines of standard systemic chemotherapy. Patients will also be eligible if they discontinued first-line or second-line therapy due to intolerance.

The study will consist of a Screening Period (Day –28 to Day –1), a Treatment Period, a Treatment Discontinuation Visit occurring \leq 30 days after the last dose of study medication, and a Follow-Up Period. Day 1 (baseline) will be defined as the first day the patient receives atezolizumab. It is anticipated that the trial will enroll 600 patients at 140 sites globally.

Enrolled patients will receive atezolizumab at a fixed dose of 1200 mg administered intravenously on the first day of each cycle (Figure 1). One cycle of therapy will be defined as 21 days (\pm 3 days). Atezolizumab treatment will continue until investigator-assessed loss of clinical benefit, unacceptable toxicity, investigator or patient decision to withdraw from therapy, or death (whichever occurs first).

Figure 1 Study Schema

Chemo, standard systemic chemotherapy; CNS, central nervous system; ECOG PS, Eastern Cooperative Oncology Group performance status; FFPE, formalin-fixed paraffin-embedded; IV, intravenous; L, line; NSCLC, non-small cell lung cancer; RBR, Research Biosample Repository; TKI, tyrosine kinase inhibitor.

- Patients with a previously detected sensitizing EGFR mutation or ALK fusion oncogene must have received targeted TKI therapy (no restrictions on number or sequence) followed by at least one line of standard systemic chemotherapy prior to receiving atezolizumab. Patients will also be eligible if they discontinued first-line or second-line therapy due to intolerance.
- Response will be assessed by the investigator using RECIST v1.1 and modified RECIST. Patients who continue atezolizumab treatment beyond radiographic disease progression assessed per RECIST v1.1 will be monitored with a follow-up scan at the next scheduled tumor assessment when the scan frequency is every 6 weeks, and will be assessed by modified RECIST criteria until treatment discontinuation. If the scan frequency is every 9 weeks, a follow-up scan is recommended at 9 weeks or earlier if clinically indicated.
- In those patients for whom tumor assessments are performed as part of local clinical practice and are available for report after PD or atezolizumab treatment discontinuation, best overall response (BOR) and PFS will be assessed from the first date of the new anticancer therapy to the end of the study per RECIST v1.1 and modified RECIST.

The primary objective of the study is to evaluate the long-term safety of atezolizumab. Long-term safety will be assessed by monitoring the nature, severity, duration, frequency and timing of atezolizumab-related SAEs and atezolizumab-related irAEs. An irAE is defined as any adverse event of special interest (AESI) associated with systemic corticosteroid use within 30 days of the onset date. All-causality AEs, all-causality SAEs, AEs and SAEs leading to atezolizumab interruption or discontinuation, and AESIs will also be reported, as well as causes of death, vital signs, physical findings and clinical laboratory results.

Secondary objectives will assess the efficacy of atezolizumab. The main efficacy objective will be to evaluate the OS rate 2 years after the first dose of atezolizumab. Other efficacy objectives will include evaluation of OS, OS rate at 3 years, PFS, ORR, and DOR (additional efficacy assessments may occur on an exploratory basis). All antitumor response assessments will be based on RECIST v1.1 and modified RECIST.

Exploratory objectives will include evaluation of the safety and efficacy of atezolizumab in patient subgroups differentiated by: presence or absence of CNS metastases at baseline; ECOG performance status; histological subtype; history of or current autoimmune disease; and prior anticancer treatment. Other exploratory and PRO outcomes will include objective response rate and progression-free survival (PFS2) following start of new anticancer therapy, HR QoL as measured on the EORTC LQ-LC13, health utility score as measured on the EQ-5D-5L instrument, and expression of PD-L1 protein and cancer-related genes in tumor samples obtained before treatment. Finally, exploratory biomarkers may be assessed in tissue to assist in the potential development of new diagnostic assays and to assess biomarkers in terms of prognosis, response/resistance and safety.

Following discontinuation of study treatment, safety assessments will be conducted for 30 days after the last study drug administration or until initiation of other anti-cancer therapy (whichever occurs

first). Thereafter, follow-up information on disease progression (unless this has already occurred), anti-cancer therapy and survival will be collected via telephone contact, patient medical records, and/or clinic visits approximately every 3 months until death, loss to follow-up, end of study (30 months after last patient in), patient withdrawal or study termination by the Sponsor, whichever occurs first.

In those patients for whom tumor assessments are performed as part of local clinical practice and are available for report after PD or atezolizumab treatment discontinuation, overall response rate (ORR) and progression-free survival (PFS) will be assessed from the first date of the new anticancer therapy to the end of the study. These data will be used in an exploratory fashion to assess whether prior atezolizumab treatment positively influences response to subsequent anticancer therapies.

An Independent Data Monitoring Committee (iDMC) will be established to review all AEs, irAEs, SAEs, AESIs and other cumulative safety data.

A Schedule of Assessments for this study is provided in Appendix 1.

Number of Patients

This study will enroll approximately 600 patients with Stage IIIb or Stage IV NSCLC who have progressed following standard systemic chemotherapy (including if given in combination with anti-PD-1 therapy or after anti-PD-1 as monotherapy). Patients with a previously detected sensitizing EGFR mutation or ALK fusion oncogene must have received targeted therapy followed by one line of standard systemic chemotherapy prior to receiving atezolizumab. Overall, patients should not have received more than two lines of standard systemic chemotherapy. Patients will also be eligible if they discontinued first-line or second-line therapy due to intolerance. The recruitment of 600 patients is expected to take place over approximately 18 months. Patients who discontinue the study prior to study treatment initiation will not be replaced.

Target Population

Inclusion Criteria

Patients must meet the following criteria for study entry:

1. Signed Informed Consent Form
2. Age \geq 18 years
3. Able to comply with the study protocol, in the investigator's judgment
4. Histologically or cytologically documented Stage IIIb or Stage IV NSCLC that has progressed following standard systemic chemotherapy (including if given in combination with anti-PD-1 therapy, after anti-PD-1 as monotherapy, or after TKI therapy). Patients with a previously detected sensitizing EGFR mutation or ALK fusion oncogene must have received targeted therapy (TKI), followed by at least one line of standard systemic chemotherapy, prior to receiving atezolizumab. Overall, patients should not have received more than two lines of standard systemic chemotherapy. Patients who have discontinued first-line or second-line therapy due to intolerance are also eligible
 - Staging must be according to the UICC/AJCC system, 7th edition (Detterbeck et al. 2009)
 - Pathological characterization may be conducted on tumor specimens from earlier stage disease, but the tumor samples must be sufficient to distinguish squamous or non-squamous histology
 - Chemotherapy regimens will be counted based on interval disease progression, and not on the number of agents or the number of switches in agents (e.g., a first-line or second-line therapy that consists of several cycles of a platinum doublet and subsequent maintenance therapy that introduces or switches to a new chemotherapy agent without interval disease progression will all be considered one chemotherapy regimen)
 - Patients with a previously-detected sensitizing EGFR mutation must have experienced disease progression (during or after treatment) on an EGFR TKI (erlotinib, gefitinib, osimertinib, etc.)
 - Patients with a previously detected ALK fusion oncogene must have experienced disease progression (during or after treatment) with crizotinib, alectinib, or another ALK inhibitor
 - Prior radiation therapy is allowed, provided that the patient has recovered from any toxic effects thereof. Combined radiation/chemotherapy treatment constitutes a single regimen
 - Combined radiation/chemotherapy treatment (chemoradiation) counts as one prior chemotherapy regimen if < 6 months have elapsed between the last dose and the date of recurrence

- Adjuvant/neoadjuvant chemotherapy is not counted as a line of treatment
- Debulking surgery and anticancer agents used for pleurodesis are not counted as lines of therapy

5. The last dose of prior systemic anticancer therapy must have been administered \geq 21 days prior to study treatment initiation
6. The last dose of prior anti-PD-1 therapy must have been administered
 - Nivolumab must have been discontinued \geq 14 days and pembrolizumab \geq 21 days prior to study treatment initiation, providing that these treatments were not administered in a clinical trial setting
7. Measurable disease, as defined by Response Evaluation Criteria for Solid Tumors, Version 1.1 (RECIST v1.1)
8. Patients with asymptomatic CNS metastases (treated or untreated), as determined by CT or MRI evaluation during screening and prior radiographic evaluation, are eligible
9. ECOG performance status 0, 1, or 2 [Appendix 7]
10. Life expectancy \geq 12 weeks
11. Adequate hematologic and end-organ function, defined by the following laboratory results obtained within 2 weeks prior to the first study treatment:
 - Absolute neutrophil count \geq 1500 cells/ μ L (without granulocyte colony-stimulating factor support within 2 weeks prior to the first study treatment)
 - White blood cell count $>$ 2500/ μ L
 - Lymphocyte count \geq 500/ μ L
 - Platelet count \geq 100,000/ μ L (without transfusion within 2 weeks prior to the first study treatment)
 - Hemoglobin \geq 9.0 g/dL (patients may be transfused or receive erythropoietic treatment to meet this criterion)
 - Aspartate transaminase (AST), alanine transaminase (ALT), and alkaline phosphatase \leq 2.5 times the upper limit of normal (ULN), with the following exceptions:
 - Patients with documented liver metastases: AST and/or ALT \leq 5 \times ULN
 - Patients with documented liver or bone metastases: alkaline phosphatase \leq 5 \times ULN
 - Serum bilirubin \leq 1.5 \times ULN. Patients with known Gilbert's Syndrome who have serum bilirubin level \leq 3 \times ULN may be enrolled.
 - Calculated creatinine clearance \geq 15 mL/min (Cockcroft-Gault formula)
 - International normalized ratio (INR) and activated partial thromboplastin time (aPTT) \leq 1.5 \times ULN. This applies only to patients who are not receiving therapeutic anticoagulation agents
 - Patients receiving therapeutic anticoagulation agents must be on a stable dose
 - HIV-positive patients are allowed, so long as they are on stable anti-retroviral therapy, have a CD4 count \geq 200 cells/ μ L, and have an undetectable viral load at the time of screening
12. For women of childbearing potential: agreement to remain abstinent (refrain from heterosexual intercourse) or use contraceptive methods that result in a failure rate of $<$ 1% per year during the treatment period and for at least 5 months after the last dose of atezolizumab
 - A woman is considered to be of childbearing potential if she is postmenarchal, has not reached a postmenopausal state (\geq 12 continuous months of amenorrhea with no identified cause other than menopause), and has not undergone surgical sterilization (removal of ovaries and/or uterus)
 - Examples of contraceptive methods with a failure rate of $<$ 1% per year include bilateral tubal ligation, male sterilization, established, proper use of hormonal contraceptives that inhibit ovulation, hormone-releasing intrauterine devices, and copper intrauterine devices
 - The reliability of sexual abstinence should be evaluated in relation to the duration of the clinical trial and the preferred and usual lifestyle of the patient. Periodic abstinence (e.g., calendar, ovulation, symptothermal, or postovulation methods) and withdrawal are not acceptable methods of contraception

13. Patients must have recovered (i.e., improvement to Grade 1 or better) from all acute toxicities from previous therapy, excluding alopecia and toxicities related to prior anti-PD-1-therapy

Exclusion Criteria

Patients who meet any of the following criteria will be excluded from study entry:

1. Symptomatic CNS metastases
2. Spinal cord compression not definitively treated with surgery and/or radiation or previously diagnosed and treated spinal cord compression without evidence that disease has been clinically stable for \geq 2 weeks prior to study treatment initiation
3. Leptomeningeal disease
4. Uncontrolled pericardial effusion or ascites requiring recurrent drainage procedures
5. Pregnant or lactating, or intending to become pregnant during the study
 - Women who are not postmenopausal (postmenopausal defined as \geq 12 months of non-drug-induced amenorrhea) or surgically sterile must have a negative serum pregnancy test result within 2 weeks prior to initiation of study drug
6. Evidence of significant uncontrolled concomitant disease that could affect compliance with the protocol, including significant liver disease (such as cirrhosis, uncontrolled major seizure disorder, or superior vena cava syndrome)
7. Significant cardiovascular disease, such as New York Heart Association cardiac disease \geq Class III, myocardial infarction within 3 months, unstable arrhythmias, or unstable angina
 - Patients with known coronary artery disease or left ventricular ejection fraction $<$ 50% must be on a stable medical regimen that is optimized in the opinion of the treating physician, in consultation with a cardiologist if appropriate
8. Significant renal disorder requiring dialysis or indication for renal transplant
9. Treatment with any other investigational agent or participation in another clinical trial with therapeutic intent within 28 days prior to study treatment initiation
10. Major surgical procedure within 4 weeks prior to study treatment initiation or anticipation of need for a major surgical procedure during the course of the study other than for diagnosis
11. Inability to understand the local language(s) for which the EORTC QLQ-LC13 and EuroQol EQ-5D-5L questionnaires are available
12. History of severe allergic, anaphylactic, or other hypersensitivity reactions to chimeric or humanized antibodies or fusion proteins
13. Known hypersensitivity or allergy to biopharmaceuticals produced in Chinese hamster ovary cells or any component of the atezolizumab formulation
14. History of autoimmune disease (Appendix 5) are allowed if controlled and on stable treatment (i.e., same treatment, same dose) for the last 12 weeks, with the exception of:
 - Patients taking concurrent abatacept or belatacept treatment, unless therapy has been withdrawn for $>$ 8 weeks
 - Patients with a history of serious or life threatening immune-related events
 - No more than 1 concomitant autoimmune disease at the time of study entry is allowed unless one of them is:
 - Autoimmune-mediated hypothyroidism on a stable dose of thyroid replacement hormone
 - Controlled Type I diabetes mellitus on a stable dose of insulin regimen
 - A medical history of such entities as atopic disease or childhood arthralgias, where the clinical suspicion of autoimmune disease is low. In addition, transient autoimmune manifestations of an acute infectious disease that resolved upon treatment of the infectious agent are not excluded (e.g., acute Lyme arthritis)
15. Prior allogeneic stem cell or solid organ transplantation
16. History of idiopathic pulmonary fibrosis, including pneumonitis, drug-induced pneumonitis, organizing pneumonia (i.e., bronchiolitis obliterans, cryptogenic organizing pneumonia), or evidence of active pneumonitis on screening chest computed tomography (CT) scan

- History of radiation pneumonitis in the radiation field (fibrosis) is permitted

17. Active tuberculosis

- In patients who have a potentially high likelihood of latent tuberculosis (e.g., recent contact with an infectious carrier, residence in a locale with high TB burden), absence of *Mycobacterium tuberculosis* infection must be confirmed before enrollment according to local practice standards

18. Administration of a live, attenuated vaccine within 4 weeks prior to study treatment initiation

- Influenza vaccination should be given during influenza season only (e.g., approximately October to March in the Northern Hemisphere).
- Patients must not receive live, attenuated influenza vaccine (e.g., FluMist®) within 4 weeks prior to study treatment initiation or at any time during the study

19. Prior treatment with CD137 agonists or immune checkpoint blockade therapies other than anti-PD-1 therapy, including anti-PD-L1 therapeutic antibodies

20. Treatment with systemic immunostimulatory agents (including, but not limited to, interferons or interleukin-2) within 4 weeks or five half-lives of the drug, whichever is longer, prior to initiation of study treatment

- Prior cancer vaccines and cellular immunotherapy are permitted

